#### 5.1.4 Laboratory Evaluations

The following laboratory evaluations are obtained as part of routine clinic and transfusion visits, which the study team will review and record from the patient's chart.

##### 5.1.4.1 Table: Clinical Laboratory Tests

Category	Tests
Hematology	Hemoglobin, hematocrit, platelet count, WBC +/- differential, reticulocyte count, hemoglobin quantification
Liver function tests	AST, ALT, total bilirubin (total and unconjugated)
Renal function tests	BUN, creatinine
Chemistry tests	Lactate dehydrogenase
Blood bank tests	Type and screen, compatibility testing, antibody identification, direct antiglobulin test, RH genotype, extended red cell antigen profile

**5.1.4.2 Table: Study Laboratory Tests 5-12 Days After Transfusion**

Category	Tests
Hematology	Hemoglobin, hematocrit, platelet count, WBC +/- differential, reticulocyte count, hemoglobin quantification
Liver function tests	Bilirubin (total and unconjugated)
Renal function tests	BUN, creatinine
Blood bank tests	Antibody screen, antibody identification, +/- direct antiglobulin test

**5.1.5 Diagnostic Tests**

Pre-transfusion and post-transfusion laboratory studies will be monitored for anti-D re-appearance or signs of increased hemolysis (i.e. lower hemoglobin/hematocrit, lower hgb A and higher hgb S level, elevated bilirubin).

**5.2 Safety Evaluation**

Subject safety will be monitored by adverse events, vital signs, anti-D reappearance and other laboratory data (complete blood count, hemoglobin quantifications, red cell antibody evaluations). It will also include evaluation for any delays in transfusion of red cells. If a patient re-demonstrates anti-D, we will end that subject's participation and he/she will resume transfusions with D negative RBC units.

We will have a medical monitor independent of the study team who is familiar with SCD and transfusion, and blood bank procedures. The medical monitor will review safety data, including antibody screens for anti-D reappearance, and other laboratory studies, i.e blood counts and hemoglobin quantifications, for signs of transfused red cell hemolysis. Details about the units transfused, including the *RH* genotype, and the red cell antigen profile, will be reviewed.

## 6 STATISTICAL CONSIDERATIONS

This is a pilot study to determine the feasibility and safety of providing *RH* genotype matched D+ red cells to patients with SCD and anti-D who require chronic transfusion therapy.

### 6.1 Primary Endpoint

The primary endpoint is the feasibility and safety of providing *RH* genotype matched D+ red cells for patients with SCD and history of anti-D who require chronic transfusion. *RH* genotype matched red cells are currently not available clinically except for rare circumstances. Descriptive, qualitative data, i.e. anti-D reappearance and signs and symptoms of increased red cell hemolysis, or delays in transfusion, will be collected to inform future multi-center studies of *RH* genotype matched red cells designed to test the effectiveness of providing *RH* genotype matched D+ red cells for patients with SCD and history of anti-D.

Given that there is donor center scalability with *RH* genotyping if more than one institution was requesting *RH* genotype matched red cells, we would consider this matching strategy feasible if provision of matched units were possible in > 85% of the transfusion study visits without a delay in transfusion.

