### **3.2.2 Total Number of Study Sites/Total Number of Subjects Projected**

The study will be conducted at 2 investigative sites in the United States. The Children's Hospital of Philadelphia, and The New York Blood Center (no subject enrollment, providing *RH* genotyped red cell units and engaged in research activities).

Recruitment will stop when approximately 20 subjects are enrolled. It is expected that approximately 20 subjects will be enrolled to produce 18 evaluable subjects.

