### **4.2 Study Treatment Phase**

Intervention visits will be scheduled with each of the subject's transfusion visits as per the subject's clinical indication for chronic transfusion therapy. We will provide one unit of D+ *RH* genotype matched RBCs at the first transfusion study visit (Figure 3). The remainder of units will be D-, CEK-matched, and negative for all other antigens the patient is alloimmunized

---

against. In this manner, should anti-D be re-stimulated, only one unit of the 3 to 11 units required for red cell exchange will be at risk for hemolysis, and the patient would not become

**Figure 3. Example transfusion protocol for D+ patient with history of anti-D** that is not currently detectable, and requires 6 units per RBC exchange every 3 weeks. One D+ unit will be matched by *RHD* genotype and transfused at the first two study visits, and an increasing number of D+ units will be issued at consecutive RBC exchange visits. U, unit. Triangle denotes a study visit for laboratory studies including an antibody screen, CBC, hemoglobin quantification and bilirubin level

acutely anemic. If laboratory monitoring shows no anti-D re-appearance or signs of increased hemolysis, the patient will receive one unit of D+ *RH* genotype matched RBCs at the 2nd transfusion study visit, and again if no anti-D re-appearance or signs of increased hemolysis, we will increase by one D+ unit per study visit until all units are D+. If a patient re-demonstrates anti-D, we will end that subject's participation and he/she will resume transfusions with D negative RBC units.

All patients with SCD on chronic transfusion therapy have a pre-transfusion complete blood count (CBC), Hgb quantification to determine %hgb A and S levels, and an antibody screen. We will collect a pre-transfusion sample to prospectively store plasma on all study subjects. Patients undergoing chronic red cell exchange will have an immediate post-procedure CBC and hgb quantification as standard of care. Study participants will return 5-12 days post-transfusion for a CBC/reticulocyte count, hgb quantification, bilirubin level, and antibody screen to evaluate for anti-D recrudescence or red cell hemolysis (Table 2).

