#### **4.2.3 Visit 3 plus**

- Same as Visit 1, keep repeating until all units transfused are D+ or anti-D reappearance

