#### 6.2.2 Efficacy Analysis

The primary efficacy endpoints will be anti-D re-appearance, signs of increased hemolysis, and timely issue of units for transfusion. These will be descriptive data.

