### 6.3 Sample Size and Power

The sample size for this feasibility and safety study is based on our current chronically transfused patient population who receive apheresis *and* have a historical anti-D, which is approximately 20-25 active patients. We expect an additional 2-3 eligible patients per year. Therefore, we anticipate that with ~20 subjects will enroll over the 5 years of the study.

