### 6.4 Interim Analysis

If a patient re-demonstrates anti-D, we will end that subject's participation and he/she will resume transfusions with D negative RBC units. If a patient's genotype precludes readily identified *RH* genotype matched RBC units and a delay in transfusion is documented in 3 consecutive visits, we will consider termination of study participation for that individual.

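### The >85% feasibility rule in section 6.1 is read off a pooled visit percentage with no interval and no patient-level summary, although supply failures can cluster by patient and repeated delays can end a patient's contribution

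*Combined protocol and SAP*

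**What the plan says.** Section 6.1 gives the plan's one numeric success rule: the strategy is judged "feasible if provision of matched units were possible in > 85% of the transfusion study visits without a delay in transfusion". The other numeric limits in the protocol are stopping or withdrawal rules. Section 6.2.2 lists timely issue of units among the efficacy endpoints and adds only "These will be descriptive data". Section 6 contains no interval, error rate, unacceptable rate or per-patient summary.

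The number of patients is set by availability. Section 6.3 starts from the apheresis patients who "have a historical anti-D, which is approximately 20-25 active patients", and section 3.2.2 expects that "approximately 20 subjects will be enrolled to produce 18 evaluable subjects".

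Visits repeat within a patient. Section 4.2.3 reads "Same as Visit 1, keep repeating until all units transfused are D+ or anti-D reappearance". Section 4.2 gives one D+ unit at each of the first two transfusion visits and one more at each later visit. It says that at the first visit "only one unit of the 3 to 11 units required for red cell exchange will be at risk for hemolysis". Its worked example is a patient who "requires 6 units per RBC exchange every 3 weeks".

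Section 6.4 allows an individual's participation to be ended where the genotype makes matched units hard to find and "a delay in transfusion is documented in 3 consecutive visits". Section 3.3.2 excludes, before enrolment, patients whose genotype or antigen-negative requirements would rule out an adequate supply.

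**The concern.** A yes/no verdict is attached to a bare percentage. Three features make that percentage harder to read than it looks.

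- **Clustering.** If a patient's genotype or antibodies make matching hard at one visit, they probably do so at the next. The visits then carry less information than the same number of unrelated visits.
- **Unequal weight.** A patient with 12 visits counts three times as much as one with 4.
- **Selective loss of failing visits.** A patient who leaves after three consecutive delays stops adding failures to the denominator, while patients who are easy to match go on adding successes.

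The result is meant to inform later multi-center studies. Their planners would receive a statement that matching is feasible, without knowing how far the data support it or how many patients could not be supplied.

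**Working it through.** The plan has no power, alpha or interval to reproduce. Its only arithmetic is 18 evaluable of 20 enrolled, an implied loss of 10%.

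**Visits per patient.** D+ units run 1, 1, 2, …, U, so a patient needing U units has U + 1 visits. With U from 3 to 11 this is 4 to 12 visits. The six-unit example has 7, giving 18 × 7 = 126 or 20 × 7 = 140 visits.

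**Assumptions not in the documents.** True availability is 80% or 75%. ICC is 0, 0.1, 0.3 or 0.5. Each patient has a constant success probability drawn from a beta distribution with parameters p(1−ICC)/ICC and (1−p)(1−ICC)/ICC. Visit counts are fixed at 7 each, or mixed: two patients at each count from 4 to 12 for 18 patients, plus one with 7 and one with 8 visits for 20 patients.

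**Independent visits, exact binomial, true rate 80%.**
- 126 visits: more than 85% needs at least 108 (107/126 = 84.9%), probability 6.4%.
- 140 visits: 119/140 is exactly 85%, so at least 120 are needed, probability 5.2%.

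**Clustered visits, simulation, true rate 80%: chance of observing more than 85%.**

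| Layout | ICC 0 | 0.1 | 0.3 | 0.5 |
|---|---|---|---|---|
| 18 patients, 7 visits | 6% | 12% | 19% | 24% |
| 20 patients, 7 visits | 5% | 10% | 17% | 22% |
| 18 patients, 4-12 visits | 6% | 12% | 21% | 26% |
| 20 patients, 4-12 visits | 5% | 11% | 19% | 24% |

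At a true 75% the same layouts give about 1% at ICC 0.1, 4-6% at 0.3 and 7-10% at 0.5.

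**If every patient with three consecutive failures leaves.** At a true 80% the ranges become 12-14% (ICC 0.1), 27-32% (0.3) and 43-50% (0.5). At ICC 0.5 the pooled percentage averages about 84% although the true rate is 80%. The mean of the patients' own proportions exceeds 85% in only about 20-22% of runs.

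A fixed example shows why. Take 18 patients with 7 visits each, of whom 15 can always be matched and 3 never.
- Full follow-up: 105/126 = 83.3%, not feasible.
- The three leave after 3 failures each: 105/(105 + 9) = 105/114 = 92.1%, feasible.
- Mean of patient proportions: 15/18 = 83.3% either way.

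**Precision.** For 88% observed in 140 visits, the 95% half-width is 1.96 × √[0.88 × 0.12/140 × (1 + 6 × ICC)], and the effective number of visits is 140/(1 + 6 × ICC).

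| ICC | Half-width (points) | Lower limit | Effective visits |
|---|---|---|---|
| 0 | 5.4 | 82.6% | 140 |
| 0.1 | 6.8 | 81.2% | 87.5 |
| 0.3 | 9.0 | 79.0% | 50 |
| 0.5 | 10.8 | 77.2% | 35 |

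**The case against.** This is a single-center descriptive pilot sized by who is available, so there is no formal type I error to protect. That stands, and no hypothesis test is asked for.

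A reader might infer that the plan treats visits as independent. The documents do not support that: they compute no variance, test or interval, and a raw proportion assumes nothing about independence. What is missing is any statement of uncertainty.

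A reader might also infer that inadequate supply would be called feasible between one time in ten and one time in four. That is not a property of this trial. It requires 80% to count as inadequate and an ICC of 0.1 to 0.5, and the documents give neither.

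Nor can it be said outright that the data are worth about 20 patients rather than 140 visits, or that 88% cannot be told from 80%. At ICC 0.1 the effective number is 87.5, nearer 140 than 20, and the interval around 88% excludes 80% until ICC reaches about 0.2.

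The strength of clustering is unknown. The exclusions in section 3.3.2 trim the spread between patients, and section 6.4 describes a contingency, not an expected pattern. Matching may also become harder within a patient as the number of D+ units rises, which a constant-probability model leaves out.

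The removal figures are an upper scenario for these layouts. Section 6.4 says termination will be considered, not that it is automatic. The simulation counts every failed visit as a delay, whereas a visit served on time with standard units would not count towards the three. If a failed step is repeated, a hard-to-match patient who stays would add visits and pull the percentage down.

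Finally, adding an interval does not change the chance that the point estimate exceeds 85%. It changes what may be concluded from it.

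**Conclusion.** The point holds as a gap in how the section 6.1 verdict is supported. The rule rests on a pooled visit percentage from about 18 to 20 patients with unequal numbers of visits, and nothing in section 6 shows its uncertainty or its spread over patients. The withdrawal provision in section 6.4, when exercised, tends to raise that percentage by cutting short the contribution of the patients who are hardest to supply.

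The size depends on two assumptions the documents do not settle, the rate regarded as unacceptable and the ICC. With 80% as the true rate, the chance of passing roughly doubles between ICC 0 and 0.1 and is about four to five times as high at 0.5. With 75% as the true rate and no removal it stays at about 10% or less. Supply well below the threshold is therefore unlikely to pass unless clustering is strong and removals are frequent. A result a few points above 85% cannot be interpreted without an interval.

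**What to change.** Keep the 85% threshold. In sections 6.1 and 6.2.2:

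- Report the visit proportion with a 95% confidence interval that respects clustering by patient, either a bootstrap that resamples patients or GEE with a small-sample robust variance.
- Report beside it each patient's proportion, the mean of these over patients, and the number of patients above 85%.
- Include patients withdrawn for repeated delays in these patient-level summaries, and state how many there were.
- State the feasibility conclusion together with the interval, not on the point estimate alone.

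The cost is a few lines of text and a little analysis, with no new data, visits or patients. The reported precision will look less favourable, and a result just above 85% would be described as uncertain.

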### 6.2 Statistical Methods

#### 6.2.1 Baseline Data

Baseline and demographic characteristics will be summarized by standard descriptive summaries (e.g. means and standard deviations for continuous variables such as age and percentages for categorical variables such as gender).

#### 6.2.2 Efficacy Analysis

The primary efficacy endpoints will be anti-D re-appearance, signs of increased hemolysis, and timely issue of units for transfusion. These will be descriptive data.

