### Study Interventions and Measures:

We will provide one red cell unit of D+ *RH* genotype matched RBCs at the first transfusion study visit. The remainder of units will be provided per clinical standard of care, i.e. D-, CEK-matched, and negative for all other antigens the patient is alloimmunized against. If laboratory monitoring shows no reappearance of anti-D and no signs of increased red cell hemolysis, the patient will receive one unit of D+ *RH* genotype matched RBCs at the 2nd transfusion study visit, and if tolerated, D+ red cell exposures will increase by one unit per study visit until all units required are D+.

---

---

For subjects with a history of stroke/recurrent transient ischemic attack or other indication who require tight control of Hb S and *RH* genotyped blood is not available, standard of care serologic matched blood would be administered rather than delaying transfusion and risking higher Hb S level.

We will collect a pre-transfusion sample to prospectively store plasma on all study subjects.

Study participants will return 5-12 days post-transfusion for a CBC, reticulocyte count, hgb quantification, bilirubin level, and antibody screen to evaluate for anti-D reappearance or red cell hemolysis.

Main study outcome measures are feasibility of identifying sufficient *RH* genotype matched units (identifying sufficient *RH* genotype match red cells without delays in transfusion), and safety (no anti-D reappearance or evidence of hemolysis of transfused red cells).

---

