#### 6.2.3 Safety Analysis

All subjects entered into the study at Visit 1 will be included in the safety analysis. The frequencies of AEs by type, severity and relationship to study intervention will be summarized. SAEs (if any) will be described in detail. The analysis will be a qualitative description of AEs.

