### **9.3.2 Risk Assessment**

Risks are greater than minimal. Providing D+ RBC units to a patient with history of anti-D may cause re-appearance of the anti-D with or without transfused red cell hemolysis. *RH* genotype matched red cells provide a higher level of matching, and thus the risk of anti-D reappearing is predicted to be very low. The study was also designed to minimize the risk of harm from anti-D reappearance by transfusing D+ *RH* genotype matched units for only 1 out of a typical 3 to 8 RBC units for the first two visits, and then titrating up by one unit with each subsequent transfusion. There is the possibility that transfusion would be delayed up to 7 days to identify adequate *RH* genotype red cell units, this may cause inconvenience (waiting or rescheduling transfusion visit).

There are risks involved with red cell transfusion, i.e. allergic reaction, infection, alloimmunization, but these risks are associated with routine clinical care and not a result of the research activities.

The risks involved with a venipuncture are pain, bleeding or bruising at the venipuncture site.

---

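### Anti-D reappearance and hemolysis, the safety half of the primary endpoint, are reported without an interval or a D+ exposure summary, although zero events in 18 to 20 subjects would leave a risk of 17 to 19% open

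*Combined protocol and SAP*

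**What the plan says.** Section 6.1 makes feasibility and safety together the primary endpoint and describes the safety information this way: "Descriptive, qualitative data, i.e. anti-D reappearance and signs and symptoms of increased red cell hemolysis, or delays in transfusion, will be collected". These data are meant to inform later multi-center studies. Section 6.2.2 lists anti-D reappearance, signs of increased hemolysis and timely issue of units as the primary efficacy endpoints, and its only statement of method is "These will be descriptive data". Section 6.2.3 plans a qualitative account of adverse events and names a subject set: "All subjects entered into the study at Visit 1 will be included in the safety analysis".

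The Abstract, under Study Interventions and Measures, gives the safety outcome as "safety (no anti-D reappearance or evidence of hemolysis of transfused red cells)".

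On size, section 3.2.2 says "It is expected that approximately 20 subjects will be enrolled to produce 18 evaluable subjects" and does not define evaluable. Section 6.3 bases the number on the available clinic population, "which is approximately 20-25 active patients", and not on precision or power.

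The only numerical success criterion is the one for feasibility in section 6.1 (more than 85% of transfusion study visits). No confidence interval, confidence level or acceptable event rate for safety appears in the documents. The percentages in the stopping criteria are monitoring triggers, not estimates.

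**The concern.** Safety is worded as no events, and the report is to be qualitative. A result of no events would therefore satisfy the wording with nothing beside it to show how little 18 or 20 subjects can rule out. The result has two readers who need that information: those designing the multi-center studies, and the IRB, which under section 3.1 reviews data from at least 5 adults before children may be enrolled.

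The second gap is exposure. The number of D+ units a subject receives depends on the units needed per visit and on how far the escalation goes. A count of subjects with and without events gives the same weight to a subject who left after two D+ units and to one who completed dozens. Section 6 plans no summary by D+ units received, and it does not say whether the denominator for these two outcomes is the section 6.2.3 set or the 18 evaluable subjects of section 3.2.2.

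**Working it through.** **The plan's own figure.** The sample size has no statistical derivation to reproduce. The step from 18 to 20 fits a 10% loss (18 / 0.90 = 20), but that 10% is inferred from the same two numbers, so the agreement is not an independent check.

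**Upper limit when no event is seen.** Inputs: n = 20 and n = 18 (section 3.2.2) and n = 5 (section 3.1). The 95% level is assumed.

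- Exact (Clopper-Pearson) two-sided 95% upper limit for 0/n: 1 − 0.025^(1/n)
- Exact one-sided 95% upper limit: 1 − 0.05^(1/n)

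| Result | Two-sided 95% upper limit | One-sided 95% upper limit |
|---|---|---|
| 0/20 | 16.8% | 13.9% |
| 0/18 | 18.5% | 15.3% |
| 0/5 | 52.2% | 45.1% |

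Check: with a true risk of 16.8%, the chance of no event in 20 subjects is (1 − 0.168)^20 = 2.5%. With a true risk of 18.5%, the chance of none in 18 is (1 − 0.185)^18 = 2.5%. With a true risk of 10%, no event would be seen with probability 0.90^20 = 12.2% in 20 subjects and 0.90^18 = 15.0% in 18.

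The choice of method matters little. The Wilson two-sided upper limits are 16.1% (n = 20) and 17.6% (n = 18), and the rule of three gives 15.0% and 16.7%. A single event in 20 has an exact two-sided 95% interval of 0.1% to 24.9%.

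**Exposure over the escalation.** Section 4.2 gives one D+ unit at each of the first two transfusion visits and then one more per visit until all units are D+. With U units per visit, that is U + 1 visits and 1 + U(U + 1)/2 D+ units.

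| Units per visit (source) | Transfusion visits | D+ units for a completer |
|---|---|---|
| 3 (inclusion minimum, section 3.3.1) | 4 | 1 + 3×4/2 = 7 |
| 6 (Figure 3 example) | 7 | 1 + 6×7/2 = 22 |
| 8 (top of the typical range, section 9.3.2) | 9 | 1 + 8×9/2 = 37 |
| 11 (top of the range in section 4.2) | 12 | 1 + 11×12/2 = 67 |

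Over the typical range, exposure among completers varies 37/7 = 5.3-fold. Over the full range it varies 67/7 = 9.6-fold. A subject on 8 units per visit who leaves after two transfusions has had 2 of 37 D+ units, about 5% of the planned exposure, and would still count as event-free.

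**The case against.** The best defence is that this is a declared pilot, sized by availability, with no safety hypothesis or threshold. A descriptive analysis suits such a study, the word does not forbid intervals, and anyone given the count and the denominator can compute one later. Much of this stands: nothing here calls for a test, a power calculation or more subjects. But an interval is itself descriptive, nothing in the documents commits to one, and sections 6.1 and 6.2.3 point towards a qualitative report.

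A reader might also infer several stronger things that the documents do not support.

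- *That the plan will conclude the risk is very low.* The sentence in section 9.3.2, "the risk of anti-D reappearing is predicted to be very low", is a prediction made beforehand from the closer matching. The same section calls the risks greater than minimal. The Abstract's phrase labels an outcome; it is not a formal rule for declaring safety.
- *That early and late events could not be told apart.* They could. D+ exposure is set by visit, an antibody screen follows each transfusion at 5 to 12 days, and section 7.1.5 has unit records extracted for the study. What is missing is a planned summary.
- *That there is no denominator at all.* Section 6.2.3 names subjects entered at Visit 1, and section 4.2.1 makes Visit 1 the first D+ transfusion. Two doubts remain: Table 1 numbers screening as visit 1, and section 6.2.3 is written for adverse events while these outcomes sit in section 6.2.2.
- *That an exact Poisson rate per D+ unit would solve the exposure problem.* Twenty completers at 6 units per visit give 20 × 22 = 440 D+ units, and zero events would give an upper limit of 3.69/440 = 0.84 per 100 units. That treats units within a patient as independent. Anti-D reappearance is a patient-level response that ends participation, so the figure would make zero events look far more reassuring than 0/20 does.

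**Conclusion.** The point holds as a gap in reporting precision on a primary endpoint, not as an error in a stated figure or in the design. Followed as written, the plan could report no events with nothing to show that a per-subject risk of up to 16.8% (n = 20) or 18.5% (n = 18) remains compatible with that result. At a one-sided 95% level the figures are 13.9% and 15.3%, and the conclusion is the same. The limits rest on an assumed 95% level and on subjects being independent.

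The unequal exposure (7 to 37 D+ units over the typical range, up to 67 at the extreme) is a supporting point. It assumes that the escalation is completed without interruption and that units per visit stay constant.

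The stopping limit for anti-D reappearance cannot serve as a benchmark for an acceptable rate. Sections 4.2 and 9.3.1 put it at more than 30% of enrolled patients, and section 8.1 at more than 50%. Those sections must be reconciled.

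**What to change.** 1. In sections 6.2.2 and 6.2.3, report the number and proportion of subjects with anti-D reappearance, and separately with hemolysis, among all subjects given at least one D+ unit. Give an exact (Clopper-Pearson) two-sided 95% interval for each. Naming this denominator also removes the doubt over Visit 1 and the undefined evaluable subjects.
2. Add cumulative incidence by number of D+ units received, censoring subjects who stop for other reasons, and tabulate D+ units and D+ visits per subject. State that this assumes those who stop for other reasons have the same later risk as those who continue.
3. In section 6.3, state what the sample can exclude: with no events, risks above 16.8% for 20 subjects or 18.5% for 18.
4. Omit a per-unit rate, or show it only as secondary, with allowance for clustering within subject and for exit after reappearance.

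The cost is a few sentences and one table, using data the study already collects and no more patients. The downside is that the safety statement becomes more modest.
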